3.8.3. Selection of Data in the Event of Multiple Records in a Window

Depending on the statistical analysis method, single values may be required for each analysis window. For example, change from baseline by visit usually requires a single value, whereas a time-to-event analysis would not require one value per analysis window.

If multiple valid nonmissing numeric observations exist in an analysis window, records will be chosen based on the following rules if a single value is needed:

- For baseline, the last available record on or prior to the date of the first dose of study drug will be selected. If there are multiple records with the same time or no time is recorded for the same day, the average (arithmetic mean) will be used for the baseline value.
- For postbaseline visits:
 - 1) Select the record closest to the nominal day (ie, visit weeks \times 7 days) for that visit; except for posttreatment HCV RNA follow-up visits, for which the latest record in the analysis window will be selected)
 - 2) If there are 2 visits equidistant from the nominal day, the later record will be selected
 - 3) If there is more than 1 record on the selected day, the average will be taken, unless otherwise specified

If multiple valid nonmissing categorical observations exist in a window, records will be selected as follows:

- For baseline, the last available record on or prior to the date of first dose of study drug will be selected. If there are multiple records with the same time or no time recorded on the same day, the values with the lowest severity will be selected (eg, normal will be selected over abnormal)
- For postbaseline visits, follow the same rules described above for postbaseline numeric observations, except that if there are multiple records on the same day, the most conservative value will be selected (eg, abnormal will be selected over normal)

4. SUBJECT DISPOSITION

4.1. Subject Enrollment, Screen Fails, and Disposition

4.1.1. Subject Enrollment

A summary of subjects enrolled and treated will be provided for each country and investigator within country for the “SOF/VEL 4 Weeks” group for subjects in the safety analysis set.

4.1.2. Reasons for Screen Failure

Reasons for screen failure will be summarized for each screen that was performed for the study. The total number of screens and number of screen failures will be provided. Screen failures will be split into the following 2 groups:

- screen failures that did not meet eligibility criteria (with inclusion/exclusion criteria not met summarized)
- screen failures that met eligibility criteria (with reasons for non-enrollment summarized)

Percentages will be calculated for the screen failure rate (denominator is number of screens), each inclusion/exclusion criteria not met (denominator is screen fails that did not meet criteria), and reasons for non-enrollment (denominator is screen fails that met eligibility criteria). A listing of inclusion/exclusion criteria that were not met for screen failure subjects will be provided, sorted by screening ID for subjects who were screened but not treated.

4.1.3. Subject Disposition

A summary of subject disposition will be provided for “SOF/VEL 4 Weeks.” The summary will present the number of subjects enrolled, and evaluated for each analysis set (ie, safety analysis set and/or FAS analysis set).

In addition, the number and percentage of subjects in the safety analysis set who met the following criteria will be summarized:

- Completed the study treatment period
- Did not complete the study treatment period (with reasons for not completing the study treatment period)
- Completed the study
- Did not complete the study (with reasons for not completing the study)

Among subjects who completed study treatment and those who prematurely discontinued study treatment, the number and percentage of subjects will be summarized for subjects with:

- No HCV RNA at the posttreatment Week 4 assessment (ie, *No FU-4 HCV RNA Assessment*)
- HCV posttreatment Week 4 assessment but no HCV posttreatment Week 12 assessment (ie, *With FU-4 but No FU-12 HCV RNA Assessment*)

If a subject has no HCV RNA assessments beyond 21 days after the last dose of any study drug (ie, lower bound of FU-4 visit for HCV), the subject is categorized as having “*No FU-4 HCV RNA Assessment.*” If a subject has an HCV RNA value for the FU-4 assessment but does not have any observed HCV RNA assessment beyond 70 days after the last dose of any study drug (ie, lower bound of FU-12 visit for HCV), the subject is categorized as having “*With FU-4 but No FU-12 HCV RNA Assessment.*”

A summary of the number of subjects in the PK Substudy analysis set will be provided by route of administration of SOF/VEL on Study Day 1 (PO or NG) and overall as part of the PK substudy analysis.

A data listing of date of informed consent, date/time transplant ended, first posttransplant dose date/time, last dose date (study day), completed study treatment (yes/no), completed study (yes/no) and reasons for premature study treatment/study discontinuation will be provided. The last observed non-missing HCV RNA value on/prior to the date the subject stopped SOF/VEL plus 3 days will be included in this listing.

A listing of subjects who were excluded from the safety and/or FAS analysis set will be provided.

4.2. Extent of Exposure

Extent of exposure to study drug will be examined by assessing the total duration of study drug exposure and the level of adherence to the study drug regimen specified in the protocol.

4.2.1. Duration of Exposure to Study Drug

Duration of exposure to SOF/VEL will be defined as (last dose date of SOF/VEL – first dose date of SOF/VEL + 1) regardless of temporary interruptions in study drug administration. All duration of exposure will be expressed in days.

Duration of exposure to SOF/VEL will be summarized using descriptive statistics (n, mean, SD, median, Q1, Q3, minimum and maximum) and using the number (ie, cumulative counts) and percentage of subjects exposed through the timepoints: Baseline (≥ 1 Day); Week 1 (≥ 7 Days); Week 2 (≥ 14 Days); Week 3 (≥ 21 Days) and Week 4 (≥ 28 Days). A ± 3 day window for the last assessment will be applied to match with the protocol-specified visit window. Summaries will be provided by treatment group for subjects in the safety analysis set.

A by-subject listing of study drug administration will be provided for subjects in the safety analysis set.

4.2.2. Adherence to Study Drug

Adherence will be calculated for SOF/VEL as:

$$[(\text{Number of tablets taken}) \div (\text{Number of study drug tablets prescribed})] \times 100$$

Note: If calculated adherence is greater than 100%, the result will be set to 100%.

A descriptive summary (n, mean, SD, median, Q1, Q3, minimum and maximum) and the number and percentage of subjects with < 80% , ≥ 80 to < 90%, and $\geq 90\%$ adherence will be presented for the safety analysis set for subjects assigned to receive SOF/VEL for 4 Weeks.

A by-subject listing of adherence will be provided for subjects in the safety analysis set.

4.2.2.1. Calculation of Number of Tablets Prescribed for Study Drug

Subjects assigned to receive 4 weeks of SOF/VEL will require 1 tablet/day for 28 days.

4.2.2.2. Calculation of Number of Tablets Taken

The number of tablets taken for SOF/VEL during the treatment period will be calculated as the sum of (number of tablets dispensed – number of tablets returned) at each distinct dispensing period across all bottles dispensed. If a bottle is dispensed, and the bottle is returned empty, then the number of tablets returned will be entered as zero. If a bottle is dispensed but not returned (missing), the number of tablets taken from that bottle will be counted as zero.

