#### **5.1.2. Packaging and Labeling**

SOF/VEL (400 mg/100 mg) FDC tablets are packaged in white, high density polyethylene (HDPE) bottles. Each bottle contains 28 tablets and polyester packing material. Each bottle is enclosed with a white, continuous thread, child-resistant screw cap with an induction-sealed, aluminum-faced liner.

SOF/VEL bottles to be distributed to centers in participating countries shall be labeled to meet all applicable requirements of the United States Food and Drug Administration (FDA), EU Guideline to Good Manufacturing Practice - Annex 13 (Investigational Medicinal Products), and/or other local regulations.

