**Appendix 2. Study Procedures Table**

**Appendix Table 1. Screening, On-Treatment Visits**

Clinical Assessments	Screening	Pre-Surgery (if more than 48 hours from screening to transplant)	Day 1 a	Days on Treatment (±2 days)						ET/ Unscheduled e
				3	5	7	14	21	28	
Informed Consent	X									
Determine Eligibility	X	X								
Medical History	X	X								
Physical Examination	X	X								X
Height and Weight b	X	X	X							X
Vital Signs c	X	X	X	X	X	X	X	X	X	X
12-lead ECG d	X	X								
CPT and MELD Scores	X	X								
Adverse Events and Concomitant Medications	X	X	X	X	X	X	X	X	X	X
Pregnancy Prevention Counseling	X	X	X							X
Hematology & Chemistry	X	X	X	X	X	X	X	X	X	X
Coagulation (PT, PTT and INR)	X	X	X	X	X	X	X	X	X	X
CrCL calculation	X	X	X	X	X	X	X	X	X	X
HCV RNA (Plasma) e	X	X	X	X	X	X	X	X	X	X
Viral RNA Sequencing /Phenotyping Sample (Plasma)			X	X	X	X	X	X	X	X
Single Pharmacokinetic Sample						X	X	X	X	X
Pregnancy Testing f	X	X	X						X	X
Urinalysis	X	X								

Clinical Assessments	Screening	Pre-Surgery (if more than 48 hours from screening to transplant)	Day 1 a	Days on Treatment (±2 days)						ET/ Unscheduled c
				3	5	7	14	21	28	
IL28B Genotype			X							
HCV Genotype	X									
HCV, HIV, HBV Serology	X	X								
Archive Sample g			X						X	X
PPD										
PK Sub-study Collection i			X							
Study Drug Dosing			X	X	X	X	X	X	X	
Review of Study Drug Adherence and Drug Accountability j				X	X	X	X	X	X	X

- a If the transplant is completed before noon, the subject will take their first dose that day after the transplant which will be considered Day 1. If the transplant is completed after noon, the subject will take their first dose the following morning which will be considered Day 1. The planned first dose may be delayed for up to 1 day if, in the investigators opinion, delay is in the subject's medical interest. ET = Early Termination; at all unscheduled visits initiated for the purpose of confirmatory testing, a viral sequence analysis plasma sample must be obtained.
- b Weight should be done with inner clothing and without shoes and Height should be done at screening only. Height will be performed only at initial screening visit. Weight will be assessed at screening and Day 1 for CrCL calculations. CrCL calculation for all post-transplant visits will use the Day 1 weight.

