## PPD

### PPD

- i All subjects will have intensive serial PK samples drawn before the SOF/VEL dose on Day 1, then dose is given, then remaining samples are collected for 24hrs. The 24 hr sample should be collected before the dose of study drug on Day 2. Detailed instructions will be provided to each study site and will also be included in the lab manual.
- j Study drug will be reconciled at every post-Day 1 visit by the investigator in order to monitor the subject's adherence with the dosing regimen. Subjects must be instructed to bring back all bottles of study drug in the original container at every post Day 1 study visits through the end of treatment.

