**Appendix Table 2. Post-Treatment Study Visits**

Clinical Assessments a	Visit identified by Post-Treatment study week			
	Post-Treatment Week 1 (± 3 days)	Post-Treatment Week 2 (± 3 days)	Post-Treatment Week 4 (± 5 days)	Post-Treatment Week 12 (±5 days)
Weight and Vital Signs b			X	
Adverse Events and Concomitant Medications	X	X	X	
Pregnancy Prevention Counseling	X			
Hematology & Chemistry	X	X	X	X
Coagulation (PT, PTT and INR)	X	X	X	X
HCV RNA and Viral Sequencing Sample (Plasma)	X	X	X	X
Pregnancy Testing c	X	X	X	

a If a subject is in Post-treatment follow-up and undergoes liver transplant, they will continue the follow-up schedule.

b Weight should be done with inner clothing and without shoes. Vital signs include resting blood pressure, pulse, respiratory rate and temperature.

c For females of childbearing potential only: serum β-hCG at Screening, urine test thereafter. If urine is positive, confirm immediately with serum β-hCG.

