3.1.3. Safety Analysis Set

The Safety Analysis Set includes all subjects who took at least 1 dose of study drug. Subjects are grouped within the Safety Analysis Set according to the treatment they actually received.

This is the primary analysis set for safety analyses.

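### Should the SAP stop scoring an unreturned bottle as zero tablets, and cut its ±3-day exposure window to the protocol's ±2 days?

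*SAP*

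**What the plan says.** **Adherence.** SAP 4.2.2 divides tablets taken by tablets prescribed, caps the result at 100%, and tabulates subjects below 80%, from 80% to below 90%, and at 90% or more. The denominator is fixed in SAP 4.2.2.1: "Subjects assigned to receive 4 weeks of SOF/VEL will require 1 tablet/day for 28 days". The numerator in SAP 4.2.2.2 is tablets dispensed minus tablets returned, summed over dispensing periods and bottles, with this exception: "If a bottle is dispensed but not returned (missing), the number of tablets taken from that bottle will be counted as zero".

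On packaging, Protocol 5.1.2 says: "Each bottle contains 28 tablets and polyester packing material". Neither document says how many bottles a subject receives. Footnote j to Appendix Table 1 of the protocol adds: "Study drug will be reconciled at every post-Day 1 visit by the investigator". The table is produced for the Safety Analysis Set, and SAP 3.1.3 reads: "The Safety Analysis Set includes all subjects who took at least 1 dose of study drug".

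**Exposure.** SAP 4.2.1 computes duration from first and last dose dates, ignoring interruptions, and then says: "A ± 3 day window for the last assessment will be applied to match with the protocol-specified visit window". The column heading in Appendix Table 1 of the protocol, which covers Days 3 to 28, begins "Days on Treatment (±2 days", and Protocol 6.3 gives the same ±2 days. A ±3-day window appears only in Appendix Table 2, for post-treatment Weeks 1 and 2 ("Post-Treatment Week 1 (± 3 days"); Weeks 4 and 12 have ±5 days.

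**The concern.** If one bottle covers the course, losing it erases the whole numerator. The resulting 0% cannot be the subject's true adherence. Everyone in the Safety Analysis Set took at least one dose, and Protocol 6.3 has staff watch the first one, so true adherence is at least 1/28 = 3.6%. The exposure table would show about 28 days for the same person. The SAP does not say whether interim counts made at earlier visits are kept when the bottle is missing at the end.

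In a study of about 10 subjects, one such case sets the reported minimum and puts a fully dosed subject in the lowest adherence category. If that subject also relapsed, a reader might blame missed doses rather than the four-week duration, which is the question the trial asks.

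The exposure sentence looks like a plain error, because the window it cites is not the one the protocol sets for Day 28.

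**Working it through.** The plan states no adherence or exposure result to reproduce, so the check applies its rules to examples.

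**Inputs.** 28 tablets prescribed (SAP 4.2.2.1); 28 tablets per bottle (Protocol 5.1.2); N = 10 (SAP 1.3). The number of bottles or dispensing periods per subject is not given, so the patterns below are assumptions.

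**Step 1: the zero-count rule.** Adherence = 100 × tablets credited / 28. Suppose nine subjects are at 100% and one fully dosed subject, at v%, has a lost bottle. Then mean = (900 + v)/10, and the sample SD reduces to (100 − v)/√10.

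| Assumed pattern | Credited | v | Mean | SD |
|---|---|---|---|---|
| One bottle of 28, lost, no interim count kept | 0/28 | 0% | 90.0% | 31.6 |
| Two lots of 14, one lost | 14/28 | 50% | 95.0% | 15.8 |
| One bottle, 20 tablets counted as taken before the Day 21 dose and that count kept, then lost | 20/28 | 71.4% | 97.1% | 9.0 |
| Four lots of 7, one lost | 21/28 | 75% | 97.5% | 7.9 |
| Two bottles of 28, the unused spare lost | 28/28 | 100% | 100% | 0 |

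In the first four rows, 1 of 10 subjects falls below 80%. In the last row the rule gives the right answer. The median is 100% throughout.

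**Step 2: the natural replacement.** Suppose adherence were instead computed up to the last count, over tablets due by then. A subject who has taken 7 of 7 tablets at Day 7 and then disappears with the bottle scores 7/7 = 100%, while only 7/28 = 25% of the course is verified. SAP 3.8.1 expressly provides for subjects lost to follow-up with an unknown last dose date, and unreturned bottles are plausible in that group. The replacement also mixes denominators within one mean. Setting the value to missing instead leaves 9 of 10 subjects in the summary.

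**Step 3: the exposure window.** The Week 4 row counts subjects with at least 28 days, less the allowance.

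- With ±3 days: 28 − 3 = 25 days, and 25/28 = 89.3% of the course.
- With ±2 days: 28 − 2 = 26 days, and 26/28 = 92.9%.

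Only a subject with exactly 25 days changes row. The SAP uses the same 3-day allowance elsewhere: 28 ± 3 days defines completion of treatment in SAP 6.2.1 and 6.2.2, and data up to 3 days after the last dose count as on-treatment in SAP 3.8.2. If exposure alone moved to ±2, a 25-day subject would have completed treatment under SAP 6.2.2 but would not be counted at Week 4 in the exposure table. No such conflict exists now.

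**Step 4: what depends on these quantities.** The SVR12 estimate and its Clopper-Pearson interval (SAP 6.1.3) use HCV RNA results in the FAS. The subgroups in SAP 3.4 and the relapse breakdown in SAP 6.2.2 use whether study drug was completed, not the adherence percentage. The Week 4 exposure row is not an input to any of them.

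**The case for a change.** The best case for a change is that zero is not conservative in every direction. In a trial of a short course, understated adherence can excuse a relapse and so flatter the regimen. The rule may also discard counts that the protocol requires at Days 3, 5, 7, 14, 21 and 28, and the remedy would be a few sentences and some code. As for the window, a stated reason that is false should not be left in a plan.

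Part of this stands. The SAP is silent on interim counts, the 0% case follows from the plan's own numbers if one bottle is dispensed, and the reason given for ±3 days is wrong for Day 28.

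The rest carries less weight. The score measures what can be accounted for, whereas exposure is a span of dates that ignores interruptions, so the two may differ without contradiction. Reconciliation at six visits makes loss of the entire count unlikely. With about 10 subjects, an odd value would be seen next to the individual record: Listing 5.1 gives drug administration, Listing 5.2 gives accountability and adherence, and PK Listing 1 gives sparse as well as intensive concentrations. A relapse would be read against those records, not against the pooled mean.

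**Conclusion.** No change to the plan follows. Counting an unreturned bottle as zero is a pre-specified trade-off. It can understate adherence for a fully dosed subject, down to 0% if a single bottle was dispensed and no interim count is kept, but the alternatives overstate adherence or drop the subject. The effect is confined to a descriptive table and arises only if a bottle is lost, an event for which the documents give no frequency. A footnote giving the number of subjects with unreturned bottles is a sensible reporting choice that needs no new rule.

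The claim that ±3 days matches the protocol is a clerical slip. The window works as an analysis convention in line with the SAP's own 28 ± 3 days, and rewording its justification would alter no result. Switching that summary alone to ±2 days would move only a 25-day subject and would introduce an inconsistency.

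The adherence figures rest on N = 10, nine subjects at 100% and the assumed dispensing patterns. The conclusion that the efficacy results are unaffected does not depend on those assumptions.

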4.3. Protocol Deviations

A listing of important protocol violations will be provided by the Clinical Operations group for subjects in the Safety Analysis set. The listing will include the criteria not met and related comments.

5. BASELINE DATA

5.1. Demographics and Baseline Characteristics

Subject demographic and baseline characteristics will be summarized for the SOF/VEL 4 Week group for subjects in the Safety Analysis Set using descriptive statistics (n, mean, SD, median, Q1, Q3, minimum and maximum) for continuous data and by the number and percentage of subjects for categorical data. Variables to be summarized include the following:

- Age (on date of first dose of study medication) as a continuous variable and for categories (< 60 and ≥ 60 years)
- Sex at birth (male, female)
- Race (White, Black or African American, Asian, American Indian/Alaska Native, Native Hawaiian/Pacific Islander, Other)
- Ethnicity (Hispanic or Latino, Not Hispanic or Latino)
- Baseline body mass index (BMI) as a continuous variable and for categories (< 30 kg/m², ≥ 30 kg/m²)
- Pretransplant HCV genotype
- Pretransplant IL28B (CC, CT, TT)
- Pretransplant HCV RNA as a continuous variable and for categories (< 800,000 IU/mL and ≥ 800,000 IU/mL)
- Pretransplant Child-Pugh-Turcotte (CPT) class
- Pretransplant CPT score (eg. 5, 6, 8) as a categorical variable
- Pretransplant native model for end stage liver disease (MELD) score as a continuous variable and as a categorical variable for individual MELD scores
- Pretransplant hepatocellular carcinoma (HCC) (yes, no)
- Pretransplant Exception MELD (from liver transplant eCRF) as a continuous variable
- Donor Type (living, cadaveric brain death, cadaveric cardiac death)
- Cadaveric Donor Type (split, whole)
- Prior HCV treatment (yes, no)

- Response to last HCV treatment regimen (non-responder, relapse/breakthrough, early discontinuation)
- Last HCV treatment regimen (pegylated interferon [PEG], PEG+RBV)
- Baseline HCV RNA as a continuous variable and for categories (< 800,000 IU/mL and ≥ 800,000 IU/mL)
- Baseline alanine aminotransferase (ALT) as a continuous variable (absolute value) and for categories (≤1.5 × upper limit of normal [ULN] and > 1.5 × ULN)
- Baseline creatinine clearance (CrCL) using the Cockcroft-Gault formula (using for weight the lesser of ideal body weight and actual body weight)

Age of the patient will be calculated as the integer of age in years on the date of first dose of study medication.

Pretransplant CPT and native MELD scores will be listed by nominal visit (eg, screening and pre-surgery) and will be calculated using the following formulas:

CPT score is calculated as: the sum of the scores related to the 5 items in the table below (if any of the components are missing, the score is not calculated):

MEASURE	1 point	2 points	3 points
Total Bilirubin (mg/dL)	< 2	2-3	> 3
Serum Albumin (g/dL)	> 3.5	2.8 – 3.5	< 2.8
International normalized ratio for prothrombin time (INR)	< 1.7	1.7 – 2.3	> 2.3
Ascites	None	Slight/Moderate (medically controlled)	Severe (medically uncontrolled)
Hepatic Encephalopathy	None	Slight/Moderate (medically controlled)	Severe (medically uncontrolled)

Native MELD score is calculated as:

$$10 \times \{[0.957 \times \text{Ln}(\text{Scr})] + [0.378 \times \text{Ln}(\text{Tbil})] + [1.12 \times \text{Ln}(\text{INR})] + 0.643\}$$

Where Scr = serum creatinine (in mg/dL), Tbil = Total Bilirubin (in mg/dL), INR = international normalized ratio, and Ln = natural log. If any lab value is less than 1.0, then set to 1.0 in the calculation. If the subject received dialysis at least twice in the past week, or if the serum creatinine value is > 4.0, then Scr is set to 4.0 mg/dL in the above formula. The result will be rounded to the nearest whole number.

MELD Exception score

At this site in New Zealand, subjects with HCC eligible for liver transplantation may be awarded additional MELD score points if they meet exception point criteria. Subjects will have an exception score of 22 assigned if they have a single HCC lesion greater than 2 centimeters or more than 1 lesion of any size. Two additional points are awarded every 3 months that the subject is on the liver transplant waitlist.

The laboratory collection date for each laboratory test used to calculate the pretransplant MELD and CPT scores are collected on the MELD/CPT eCRF form and are to be merged, individually for each laboratory test with the laboratory collection date on the COVLAB dataset to obtain the numeric result for the test.

By-subject listings of demographic and baseline characteristics will be provided for subjects in the safety analysis set.

A separate by-subject listing for prior HCV treatment and response will be provided.

A by-subject listing of transplant information and donor organ characteristics will be provided for subjects in the FAS and will include: transplant start and end date/time, hours and minutes (HH:MM) of cold/ischemia time, pretransplant HCC (yes/no), pretransplant MELD native score, pretransplant MELD exception score (when applicable), donor type, cadaveric donor type, cause of donor death, donor age/sex/race/ethnicity [when available], donor hepatitis C nucleic acid amplification test (NAT) status, and location of organ (local, regional, national).

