### 6.9.5. MELD Score/Child-Pugh Score

MELD Score and Child-Pugh-Turcotte score should be assessed at Screening and on Day 1.

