**Table 6-1. Child-Pugh-Turcotte Classification of the severity of cirrhosis**

	Points		
	1	2	3
Encephalopathy	None	Grade 1-2 (medication-controlled)	Grade 3-4 (medication-refractory)
Ascites	None	Mild/Moderate (diuretic-responsive)	Severe (diuretic-refractory)
Bilirubin (mg/dL)	< 2	2-3	> 3
Albumin (g/dL)	> 3.5	2.8-3.5	< 2.8
INR	< 1.7	1.7-2.3	> 2.3

Note: if the either ascites or encephalopathy is “none” because the patient is taking medication which has controlled the symptoms, the scoring should be 2 points (not 1 point).

CPT score is obtained by adding the points for each parameter

CPT class is scored as:  
 A = 5-6 points  
 B = 7-9 points  
 C = 10-15 points

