## MELD Score Calculation

The MELD score is calculated as:

$$10 \times \{[0.957 \times \text{Ln}(\text{Scr})] + [0.378 \times \text{Ln}(\text{Tbil})] + [1.12 \times \text{Ln}(\text{INR})] + 0.643\}$$

Where Scr = serum creatinine (in mg/dL), Tbil = Total Bilirubin (in mg/dL), INR = international normalized ratio, and Ln = natural log. If any lab value is less than 1.0, then set to 1.0 in the calculation. If the subject received dialysis at least twice in the past week, then Scr is set to 4.0 mg/dL in the above formula. The result will be rounded to the nearest whole number.

For the components of the MELD score and the components of the CPT score which are based on laboratory values, the data will be obtained from the central laboratory, and the scores will be calculated within the clinical database.

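### SAP Section 5.1 leaves out the protocol's 2-point rule for ascites or encephalopathy that is absent only because of medication, so pretransplant Child-Pugh scores may be understated by 1 to 2 points

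*SAP*

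**What the plan says.** **CPT scoring.** SAP Section 5.1 gives the CPT score by this rule: "the sum of the scores related to the 5 items in the table below (if any of the components are missing, the score is not" computed). For ascites and encephalopathy its table gives 1 point for None and 2 points for "Slight/Moderate (medically controlled"). No note follows the table. Protocol Table 6-1 has the same five items, but adds that where either sign is none "because the patient is taking medication which has controlled the symptoms, the scoring should be 2 points (not 1 point").

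**Class.** SAP Section 5.1 lists "Pretransplant Child-Pugh-Turcotte (CPT) class" among the baseline variables but gives no cut-offs. The protocol does, under Table 6-1: A is 5–6, B is 7–9, C is 10–15.

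**MELD.** Both documents use the same formula. The protocol's creatinine rule is "If the subject received dialysis at least twice in the past week, then Scr is set to 4.0 mg/dL". The SAP keeps that rule and adds a second trigger: "or if the serum creatinine value is > 4.0, then Scr is set to 4.0 mg/dL in the above formula".

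**Visits.** Protocol Section 6.9.5 says "MELD Score and Child-Pugh-Turcotte score should be assessed at Screening and on Day 1". The protocol synopsis and Appendix 2 (Appendix Table 1) place both scores at Screening and Pre-Surgery, and Appendix 2 has no mark at Day 1. SAP Sections 3.8.2 and 5.1 follow the synopsis and Appendix 2.

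**The concern.** Read literally, the two CPT rules score the same finding differently. A waitlisted patient with no current ascites on diuretics, or no current encephalopathy on treatment, earns 2 points for that item under the protocol and 1 under the SAP. The error runs one way: the SAP can only make subjects look less sick.

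CPT class, CPT score and native MELD are the severity descriptors in SAP Table 4 and Listings 25 and 26. A reader of the study report will use them to judge how advanced the liver disease was. The SAP does not mention that its rule differs from the protocol's. Sections 6.4 and 7.8 report no changes to the efficacy and safety analyses, and no section covers changes to baseline derivations.

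**Working it through.** The plan states no figure for this point that could be reproduced, so the check compares the two scoring rules.

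**Inputs.** Item scores and the note are from protocol Table 6-1; the SAP item scores are from Section 5.1; the class cut-offs are the protocol's.

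**Worked example.** Both signs are absent on controlling medication, and bilirubin, albumin and INR each score 1.
- Protocol: 2 + 2 + 1 + 1 + 1 = 7, class B.
- SAP: 1 + 1 + 1 + 1 + 1 = 5, class A.

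**When the class changes.** Let k be the number of signs affected. Then protocol score = SAP score + k. I let every other item take 1, 2 or 3 points and classified both totals.

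| Signs affected | Combinations | Class differs | SAP score at which it differs |
|---|---|---|---|
| 1 | 3^4 = 81 | 23 | 6 (protocol 7, A instead of B): 4; 9 (protocol 10, B instead of C): 19 |
| 2 | 3^3 = 27 | 17 | 5 or 6 (A instead of B): 1 + 3; 8 or 9 (B instead of C): 7 + 6 |

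The class never differs by more than one. These are counts of score patterns, not probabilities for patients; the documents give no frequency of medication-controlled signs.

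**Weight in the table.** With 10 subjects, one reclassified subject is 1/10, or 10 percentage points.

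**MELD cap, checked separately.** For creatinine above 4.0 mg/dL, the SAP lowers MELD before rounding by 10 × 0.957 × ln(Scr/4) = 9.57 × ln(Scr/4). At or below 4.0 the difference is 0. For creatinine values assumed for illustration:
- 4.5 mg/dL: 1.1 points
- 5.0 mg/dL: 2.1 points
- 6.0 mg/dL: 3.9 points

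Creatinine is not a CPT item, and neither document defines MELD classes, so the cap cannot move a class.

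**Visits.** Section 6.9.5 conflicts with the protocol's own synopsis and Appendix 2. Day 1 follows the transplant (Section 6.2.2), so a Day 1 score cannot describe pretransplant severity. The general SAP baseline rule (Section 3.8.2) takes the last value on or before first dose. First dose also follows the transplant, so that rule alone does not settle which score enters SAP Table 4; only the word pretransplant in the variable name points to it.

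**The case against.** The strongest reply is that the SAP sum may already be right in practice. Ascites and encephalopathy are clinical grades. Protocol Section 6.9.5 draws only the laboratory components from the central laboratory, and SAP Section 5.1 merges only laboratory results onto the MELD/CPT form. Sites work from the protocol, so a site that applies the Table 6-1 note will enter the 2-point grade, and the SAP will add it correctly. The SAP's 2-point label, "Slight/Moderate (medically controlled"), can also be read as covering these patients.

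The first part stands as a real condition: the form is not among the documents, so an error cannot be asserted outright. The second part is weaker. The protocol's own 2-point labels also refer to medical control, yet its authors still added a note for none. The label was evidently not thought sufficient.

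On the cap, hemodialysis before or at transplant is an exclusion (Section 4.3), so creatinine above 4.0 should be uncommon. The SAP rule is also coherent: without it, an undialysed subject at 6.0 mg/dL would outscore a dialysed one set to 4.0. That stands, and it leaves only an unmentioned difference between the documents.

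A reader might infer from Section 6.9.5 that no usable severity data will exist close to surgery. The documents do not support that. Section 3.4 sends sites to Section 6 and Appendix 2 together. Appendix 2 schedules chemistry, coagulation, physical examination and both scores at Pre-Surgery, a visit that is skipped only when Screening itself falls within 48 hours of surgery.

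**Conclusion.** The point holds as a minor one. SAP Section 5.1 omits a scoring rule that the protocol states. If sites enter a plain None for medication-controlled signs, pretransplant CPT is understated by 1 or 2 points, and the reported class falls by exactly one when the total lies near a cut-off. If sites apply the note at entry, there is no error. The documents do not say which happens.

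Three stronger readings go beyond the documents:
- That the same patient will get a different class under the two documents: this depends on data entry and on where the total falls.
- That the MELD cap and the visit wording add to the class error: neither enters the CPT score, and on visits the SAP agrees with Appendix 2, so that conflict lies within the protocol.
- That a planned comparison with the CPT class B population of ASTRAL-4 is compromised: neither document plans one.

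CPT and MELD are baseline descriptors (protocol Section 8.4). They are not among the SVR12 subgroups in SAP Section 3.4 and enter no endpoint, so SVR12 and its interval are unaffected.

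**What to change.** In SAP Section 5.1:
1. Carry over the Table 6-1 note, so that none on controlling medication scores 2 points, taken from the site-recorded grade.
2. Add the class cut-offs (A 5–6, B 7–9, C 10–15).
3. State that SAP Table 4 uses the last score before transplant.

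Before programming, confirm how the MELD/CPT form records a medication-controlled sign. If it cannot distinguish this from a plain None, a query to the site is better than inferring control from the concomitant medication list, which would replace a clinical judgement with an unspecified algorithm.

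As separate reconciliations with no effect on class:
- Use one MELD creatinine rule in SAP Section 5.1 and protocol Section 6.9.5, or note the SAP's addition as a change.
- Reconcile the visits named in protocol Section 6.9.5 with the synopsis and Appendix 2.

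The cost is a few sentences in the SAP, one programming line and one protocol text correction. No new data are needed if the form already captures controlling medication; otherwise there are queries on about 10 subjects at about one planned centre.
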